### Primary outcomes:

**Appeal (H1)**—E-cigarette use and amount of e-cigarette product used per week, proportion of participants that report e-cigarette use at each assessment, satisfaction scores for e-cigarettes, and whether they continue e-cigarette use at 12 weeks (3w after end of trial). Correlation between change in e-cigarette use and change in cigarette use.

Combustible Tobacco Toxicity (H2)—Exhaled CO, urine NNAL and 1-hydroxy naphthaline (1- HOP). Because smokers are good at regulating nicotine intake, we expect no change in urine cotinine over time.

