## OUTCOMES ASSESSMENT

Each visit will include a checklist that assesses how the participant is using the e-cigarettes and what problems he/she may be encountering with the use of the e-cigarette device. Adverse events will be assessed with a checklist for commonly occurring side effects from e-cigarettes and nicotine products. The coordinators will conduct and audio-record a 10-15 minute qualitative interview at 9 weeks soliciting perceptions about e-cigarettes to be transcribed and analyzed for common themes that could be useful in developing the larger intervention.

*Behavioral assessments:* We will use a Timeline Follow-Back Questionnaire (TLFB) to document use of cigarettes at baseline and cigarettes/e-cigarettes at baseline, 3, 6, 9, and 12 weeks. At follow up visits participants will be instructed to bring in all used and unused e- cigarettes, in order to verify reports of e-cigarette use. We will evaluate appeal with attitudinal ratings, on a 5-point Likert-type scale, e-cigarette ease of use, satisfaction, and enjoyment, and willingness to continue to purchase e-cigarettes in the future. All questionnaires are being programmed using a secure web-based system set up and maintained by the Dartmouth Bioinformatics group led by [name].

*Biomarkers of behavior:* Cigarette smoking will also be measured with exhaled carbon dioxide. We will assess expired breath CO2 using Micro Smokerlyzer meters (Bedfont Scientific), which have already been purchased for a previous study. The protocol will follow operating instructions that come with the devices, and the devices will be calibrated weekly with 40PPM CO2/air mixture. E-cigarette smoking will be measured with urine propylene glycol, the main constituent of e-cigarette aerosol. Some 40% of ingested

propylene glycol is excreted unchanged in the urine.

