### Qualitative Analysis

A follow up interview will be conducted at week 9. The interview will be transcribed and a thematic analysis will be conducted to evaluate common issues encountered by smokers with cancer patients who use e-cigarettes. Thematic analysis consists of examination of text by identifying and grouping themes, followed by coding, classifying, and developing categories. Transcripts are uploaded into a qualitative analytic software program and analyzed using Atlas.ti, a qualitative coding program. Co-investigator [name] has experience using similar qualitative methods to interview health professionals. She will supervise the coders, staff at the Centers for Health and Aging at Dartmouth who have been trained to perform similar analyses in other studies.

*Substitution assessment:* The proportion of participants who report use of e-cigarettes during each follow-up visit during treatment will also be computed (along with a 95% confidence interval). This proportion is expected to be at least 0.5. With 40 participants, width of a 95% confidence interval around this proportion will be at most 0.32. The satisfaction with e- cigarettes (averaged across 3 treatment assessments) will be summarized among participants using descriptive statistics and the amount of e-cigarette product returned at each follow-up period will be summarized across the treatment period.

To explicitly test the substitution/replacement mechanism of e-cigarettes, we will perform an exploratory parallel process growth model fit within a structural equation modeling framework. In this model the trajectory over time of both frequency/quantity of cigarette use and frequency/quantity of e-cigarette use will be modeled assuming individual-level latent intercept and slope (i.e., latent growth curve model). A significant negative association between the latent slope of e-cigarettes and the latent slope of combustible cigarettes would be consistent with the replacement/substitution hypothesis. The model provides an explicit statistical test of the hypothesis that, as e-cigarette usage increases, combustible cigarette usage decreases. Power for this analysis is computed as that for an individual-level correlation coefficient assuming 40 participants. There will be at least 80% power to detect a correlation that is at least -0.4 between these two individual-level slopes. Figure 7 shows a diagram of the parallel process growth model.

n

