**Toxicity Assessment:** Our measures of toxicity, urine NNAL, 1-HOP and CO2 will be compared between the baseline and 9-week assessments via paired t-test. For NNAL, assuming a standard deviation of change in this measure of 3.8 pmol/mg creatinine (as was seen in Joseph et al. 2008), with 40 participants, this test will have 80% power at the two-sided 0.05 significance level to detect a change from baseline of 1.7 pmol/mg creatinine. There is not enough information available on 1-HOP to perform a test of power, so analysis of this metabolite is considered exploratory. For expired CO, assuming a standard deviation of change in this measure of 17.0 ppm, with 40 participants, a paired t-test comparing baseline to 9-week will have 80% power at the two-sided 0.05 significance level to detect a change from baseline that is 7.7 ppm. Additionally, since CO2 will be measured several times throughout the treatment period, the trajectory of change over time in this measure will be modeled via linear mixed effects models including random intercept and slope terms to account for repeated observations within individual. With repeated measurements of CO, the power for the mixed model will be greater than that of the paired t-test of change from baseline to detect this change over time.

We will also evaluate toxicity by analyzing cotinine level to assure that the adverse effect of increased cotinine (resultant from increased e-cigarette usage without similar decrease in combustible cigarettes). To do this, we will compute the number of participants with an increase in cotinine over the course of the study and consider this an adverse event. With 40 participants, confidence intervals around this adverse event percentage will be at most 0.32 percentage points. The table below gives the probability of observing at least 1 participant with an increase in cotinine given different true percentage of participants with this adverse event. For example, if the population-wide true percentage of participants with cotinine increase is 0.5%, then the probability of observing at least 1 of the 40 study participants with an increase is 0.18.

True percentage of participants with increase cotinine	Probability of observing at least 1 adverse event (increase in cotinine)
0.5%	0.18
1%	0.33
2%	0.55
5%	0.87
10%	0.99

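### The cotinine count is justified by added e-cigarette use without a matching fall in cigarettes, but it counts every rise and does not separate rises by use of either product

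*Combined protocol and SAP*

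**What the plan says.** The cotinine analysis is the second part of the Toxicity Assessment paragraph in the Statistical Analysis section. It opens with "We will also evaluate toxicity by analyzing cotinine level" and gives, in parentheses, the adverse effect that prompts it: a cotinine increase "resultant from increased e-cigarette usage without similar decrease in combustible cigarettes". The next sentence turns this into a rule, to "compute the number of participants with an increase in cotinine over the course of the study and consider this an adverse event".

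The precision statement is "With 40 participants, confidence intervals around this adverse event percentage will be at most 0.32 percentage points". A table then gives the chance of seeing at least one event; at a true rate of 0.5%, for example, "the probability of observing at least 1 of the 40 study participants with an increase is 0.18". The rule, the worked example and the table all describe the event only as an increase in cotinine.

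Three other places bear on the point:

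- Under Primary outcomes, the plan states that "we expect no change in urine cotinine over time".
- For the share of participants reporting e-cigarette use at each follow-up visit during treatment, the substitution assessment says "This proportion is expected to be at least 0.5".
- Under Outcomes Assessment, the timeline follow-back (TLFB) questionnaire will "document use of cigarettes at baseline and cigarettes/e-cigarettes at baseline, 3, 6, 9, and 12 weeks", and urine propylene glycol is named as a measure of e-cigarette use.

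The visit table lists urine at baseline, week 3 and week 9.

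**The concern.** The rationale names both products and the rule names neither. No other section ties the count to product use. A participant who never took up the e-cigarette and smoked more would be entered under toxicity in the same way as one who added e-cigarettes to unchanged smoking.

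There is no control arm to show how many rises would occur without the product. The participant's own use data are therefore the only means of telling these cases apart, and the rule does not use them. A reader of the final percentage could take it as the rate of the effect in the parentheses, when an unknown part of it need not involve the product. The pilot is meant to inform a larger randomised trial, so that misreading could be carried forward.

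**Working it through.** **The plan's own figures.** The table is P(at least 1) = 1 − (1 − p)^40.

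| True rate p | Plan | Recomputed |
|---|---|---|
| 0.5% | 0.18 | 0.1817 |
| 1% | 0.33 | 0.3310 |
| 2% | 0.55 | 0.5543 |
| 5% | 0.87 | 0.8715 |
| 10% | 0.99 | 0.9852 |

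The stated maximum interval width of 0.32 also reproduces, as a proportion: with 20 of 40 events the exact 95% interval is 0.338 to 0.662, a width of 0.324. The arithmetic is sound. It holds for any yes/no event, so it does not depend on how the event is defined.

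**Rationale against rule.** Take three participants with the same cotinine rise.

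| Participant | Counted by the rule | Fits the rationale |
|---|---|---|
| No e-cigarette use, cigarettes 20 to 25 per day | Yes | No |
| Daily e-cigarette use, cigarettes 20 to 2 per day | Yes | Unclear |
| Daily e-cigarette use, cigarettes 20 to 20 per day | Yes | Yes |

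Only the first is securely outside the rationale.

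**Non-user share of counted events.** Let u be the share using e-cigarettes at the visit and r the chance of a cotinine rise. Assume r is the same in users and non-users.

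- Counted events = 40 × r
- Counted events in non-users = 40 × r × (1 − u)
- Non-user share = 1 − u, whatever the value of r

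The documents give u only as an expectation of at least 0.5. They give no r. With no true change and a symmetric change from baseline to week 9, r = 0.5; a value of 0.3 is shown as a second assumption.

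| u | Non-user share | Non-users among counted, r = 0.5 | r = 0.3 |
|---|---|---|---|
| 0.5 | 50% | 10 of 20 | 6 of 12 |
| 0.7 | 30% | 6 of 20 | 3.6 of 12 |
| 0.9 | 10% | 2 of 20 | 1.2 of 12 |

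**Sensitivity to a real product effect.** Suppose a quarter of users add nicotine, raising cotinine by 50%, with a within-person log SD of 0.3 per sample. All three figures are assumptions. An adder's chance of a rise is Φ(ln 1.5 / (0.3 × √2)) = Φ(0.956) = 0.83; everyone else's is 0.5.

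- u = 0.5: non-users 20 × 0.5 = 10.0; other users 15 × 0.5 = 7.5; adders 5 × 0.83 = 4.15; total 21.65. Non-user share 10.0 / 21.65 = 46%.
- u = 0.9: non-users 4 × 0.5 = 2.0; other users 27 × 0.5 = 13.5; adders 9 × 0.83 = 7.47; total 22.97. Non-user share 2.0 / 22.97 = 9%.

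A true effect lowers the non-user share only slightly below 1 − u.

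**The case against.** The strongest reply is that the plan never formally defines the event by product use. The sentence holding the parentheses is grammatically incomplete and reads as a reason for watching cotinine; the event is labelled consistently as any increase. An inclusive count is a defensible choice for safety in a small single-arm pilot. NNAL, 1-HOP and the breath measure are the named toxicity measures, and no test, hypothesis or stopping rule depends on the cotinine count. All of this stands, and it limits the weight of the point. It does not remove the gap: the counting rule is presented as the means of addressing the stated effect, and it cannot isolate that effect.

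A second reply also stands. A rise in someone who cut cigarettes heavily is not clearly a miscount. The plan expects smokers to hold nicotine intake steady and lets them move e-liquid strength up or down by preference, so such a rise may be nicotine from the product. A reader might infer that substituters are wrongly counted; the documents do not support that.

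A reader might also infer that most counted events are false. That would require treating every chance rise in an e-cigarette user as a miscount, and would need figures for within-person variation, for how many users add nicotine and for change in cigarettes per day. None is given. A user with a chance rise and unchanged smoking would still be counted under a rule that used both products.

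**Conclusion.** The point holds as a mismatch between stated rationale and counting rule, with modest consequences. Rises in participants not using e-cigarettes are counted under toxicity, and nothing planned separates them from rises in dual users. If rises are unrelated to use, non-users supply about 50% of counted events at 50% use and about 10% at 90% use. These shares rest on that assumption and on the plan's expectation for use, which is not a guaranteed minimum. The actual mix cannot be derived from the documents.

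Two limits apply. The plan says toxicity and adverse event; reading the percentage as toxicity of e-cigarettes specifically is an inference, though a natural one given the parentheses. The probability table needs no change on this account. The absence of a minimum rise or a fixed comparison visit is a separate matter: setting either would not by itself separate rises by product use.

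**What to change.** Keep the count of all cotinine rises, so that no safety information is lost. For each rise, at the same urine visit (week 3 or week 9), classify the participant by TLFB e-cigarette use and by change in cigarettes per day from baseline, in three rows:

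1. no e-cigarette use;
2. e-cigarette use with reduced cigarettes;
3. e-cigarette use without reduced cigarettes.

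Set the cut for reduced cigarettes in advance. State that the third row is the event matching the rationale, and report the second row separately without calling it a miscount. Check reported e-cigarette use against urine propylene glycol, and confirm that this assay will be run, since the laboratory paragraph lists only nicotine, cotinine, NNAL and 1-HOP.

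The cost is a few sentences in the plan and one cross-tabulation. The TLFB data are already scheduled at the urine visits, and no visit or procedure changes. The downside is small: the classified event depends partly on self-report and will be rarer, and some chance rises in continuing dual users will still fall in the third row.

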## **TRIAL PROTOCOL**

### **STUDY DESIGN**

We will enroll 40 chronic smokers from the Norris Cotton Cancer Center and the White River Junction VAMC, approximately 15 of which will be accrued from the White River Junction VAMC. Participants will be given access to e-cigarettes for a 9-week period. Consecutive patients with stage I-IV aerodigestive tract cancers or bladder cancer who are current daily smokers will be identified two ways:

- 1) Clinic Recruitment - Potential participants will be identified by the treating physician during routine clinic visits. Patients will be advised to quit smoking as per the standard of care. Any patient wishing to quit smoking will be referred for smoking cessation counselling through the DHMC program, the White River Junction VAMC program, or their state help-line. Once eligibility is confirmed and informed consent is obtained and signed, patients will be enrolled in the study.
- 2) EMR Recruitment: In a recruitment strategy that parallels clinic recruitment, we will use the EMR to identify all potentially eligible smokers (with the diagnosis of aerodigestive tract cancers or bladder cancer) that have been seen in the NCCC in the past 3 years. EMR records will be searched by the D-HRDS Analytics Institute who will then forward a list of potential subjects to the project coordinator with their diagnoses and contact information, consistent with our partial HIPAA waiver. The project coordinator will then send this list of potential subjects to their providers to be approved to be contacted about the study. Approved potential subjects will then be contacted by mail through a letter from their NCCC oncology group. The subjects will have an opportunity to opt out of receiving a phone call through a prepaid return mailer or by calling a telephone number. If we do not hear from them in 2 weeks, we will then attempt to call them. We will attempt to call one time a week for 3 weeks. If there is no answer we will leave a brief, generic message. The call will assess their smoking status, and their willingness to quit. Nonsmokers are not eligible. If they smoke and are interested in quitting, they will be referred to their state quit line. If they are not interested in quitting at this time, they will be

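### The precision stated for the cotinine adverse event percentage carries the wrong unit: with 40 participants the 95% interval can be about 32 percentage points wide, not 0.32.

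*Combined protocol and SAP*

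**What the plan says.** The study is a single-arm pilot: "We will enroll 40 chronic smokers from the Norris Cotton Cancer Center" and a second site, the White River Junction VAMC (Study Design).

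The last part of the Toxicity Assessment paragraph (Statistical Analysis and Power Considerations) defines a binary safety event per participant: "we will compute the number of participants with an increase in cotinine over the course of the study and consider this an adverse event". It then states the precision for the percentage with that event: "With 40 participants, confidence intervals around this adverse event percentage will be at most 0.32 percentage points". It gives no confidence level or interval method, and does not say whether 0.32 is a full width or a half-width.

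The same section has a parallel statement in the Substitution assessment paragraph, for the proportion reporting e-cigarette use: "With 40 participants, width of a 95% confidence interval around this proportion will be at most 0.32". There the level is 95%, the quantity is a full width and the scale is a proportion.

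A short table follows the cotinine sentence. It gives the chance of seeing at least one event among 40 for true rates of 0.5%, 1%, 2%, 5% and 10%.

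**The concern.** The same number, for the same sample size, appears in two units that differ by a factor of 100. A maximum width of 0.32 is correct for a proportion estimated from 40 people. A maximum of 0.32 percentage points is 0.0032 on that scale, far below anything 40 binary observations can deliver.

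This is the only precision the plan states for the cotinine event. The adjacent table gives the probability of seeing at least one event, which is a different quantity. The sentence also does not look absurd where it stands: next to true rates of 0.5% and 1%, a figure of 0.32 points seems to be on a plausible scale and would suggest that the study can tell such rates apart. What is at stake is an accurate account of how well a 40-person pilot can estimate this percentage.

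**Working it through.** **Inputs.** n = 40 (Toxicity Assessment and Study Design). The outcome is binary: cotinine increased or not (Toxicity Assessment). The confidence level is taken as 95% from the Substitution assessment paragraph, because the cotinine sentence gives none.

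**Step 1: reproduce 0.32 as a proportion.** The interval is widest at 20 of 40. Full widths there:

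| Method | Calculation or limits | Full width |
|---|---|---|
| Normal approximation (Wald) | 2 × 1.96 × √(0.25/40) | 0.310 |
| Wald with t quantile, 39 df | 2 × 2.0227 × √(0.25/40) | 0.320 |
| Exact (Clopper-Pearson) | 0.338 to 0.662 | 0.324 |
| Jeffreys | | 0.301 |
| Wilson, Agresti-Coull | | 0.296 |

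So 0.32 is reproduced as a full width on the proportion scale, which is about 32 percentage points. As a half-width it does not fit: the maximum half-width is 0.155 (Wald) to 0.162 (exact).

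**Step 2: test 0.32 percentage points (0.0032).** No variant reproduces it as a maximum.

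- Full width: 32.4/0.32 = 101 (exact) and 31.0/0.32 = 97 (Wald), so about 100 times too narrow.
- Half-width: 16.2/0.32 = 51 (exact) and 15.5/0.32 = 48 (Wald), so about 50 times too narrow.
- A 90% level instead of 95%: the Wald full width is still 26.0 points.
- Sample size needed for a worst-case 95% Wald full width of 0.0032: (2 × 1.96)² × 0.25 / 0.0032², about 375,000. If 0.0032 were a half-width: 1.96² × 0.25 / 0.0032², about 94,000.

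**Step 3: low event counts.** Exact 95% intervals with n = 40:

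| Events | Interval | Width (points) |
|---|---|---|
| 0 | 0% to 8.8% | 8.8 |
| 1 | 0.1% to 13.2% | 13.1 |
| 4 | 2.8% to 23.7% | 20.9 |

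The upper limit at zero events is 1 − 0.025^(1/40) = 0.088. This is the narrowest exact interval, and it is still 8.8/0.32 = 27.5 times the stated maximum.

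**Step 4: check the adjacent table.** The formula is 1 − (1 − p)^40.

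| True rate | Computed | Plan |
|---|---|---|
| 0.5% | 0.182 | 0.18 |
| 1% | 0.331 | 0.33 |
| 2% | 0.554 | 0.55 |
| 5% | 0.871 | 0.87 |
| 10% | 0.985 | 0.99 |

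The table is right. The fault lies in the unit of one sentence.

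**The case against.** The strongest reply is that this is a visible slip with no consequence. The correct figure stands earlier in the same section, and no sample size, power figure, threshold or stopping rule rests on the mislabelled one. The adjacent table also already shows how little 40 participants can rule out: at a true rate of 5% it gives 0.87 for at least one event, so no event at all is seen about 13% of the time (0.95^40 = 0.129). All of this is true, and it limits the weight of the point. It does not make the sentence correct. The earlier figure concerns a different endpoint, and the table says nothing about interval width.

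A second reply is that the factor of 100 presumes a full width, which the cotinine sentence does not say. That also stands in part. Read as a half-width, the understatement is about 50-fold. The parallel sentence and Step 1 make the full width the likelier meaning, and the figure is wrong on either reading.

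A third reply is that the zero-event case may be unrealistic. The plan sets no minimum size for an increase, and Primary outcomes expects no change in urine cotinine over time. If individual changes scatter evenly around zero (an assumption; the documents give no distribution), about half the participants would show some increase. The width near 32 points would then be the relevant one. This affects which illustration is most useful, not whether the sentence is wrong.

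A reader might also infer that the monitoring committee or ethics board would be misled about safety. The documents do not support going that far. They do not say that either body relies on this figure, and other adverse events are collected by checklist (Outcomes Assessment).

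**Conclusion.** The sentence is wrong as written because of its unit. With 40 evaluable participants the 95% interval for this percentage can be about 32 points wide (exact 32.4, Wald 31.0). The stated precision is about 100 times too narrow as a full width, or about 50 times as a half-width. The calculation assumes a 95% level, borrowed from the parallel statement, and a cotinine result for all 40. Fewer evaluable participants would widen the interval: with 36, an illustrative number, the Wald maximum is 2 × 1.96 × √(0.25/36) = 32.7 points.

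It would be tempting to conclude that the pilot is undersized or its safety assessment unsound. That does not follow. The sample size, power figures and probability table do not depend on this number, and no decision rule in the plan refers to it. This is a correction to one stated precision in the statistical plan. It is worth making, and it is confined to that sentence.

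**What to change.** Replace the sentence with wording such as: 'If all 40 participants are evaluable, the 95% confidence interval for the percentage with a cotinine increase will have a full width of no more than about 0.32, that is about 32 percentage points.' Name the interval method. If it is the exact method, give the maximum as 32.4 points, because a flat bound of 32 would itself be slightly too low. Report the interval together with the observed count.

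The cost is one sentence and a less favourable statement of precision. No design element, analysis or table has to change.
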